1 SYNOPSIS

Master Protocol Title:	Platform of R andomized A daptive C linical T rials I n C ritical Illness (PRACTICAL) Randomized Control Trial
Domain Protocol Title:	Ultra-Low Tidal Volume Mechanical Ventilation in ARDS through ECMO (ULTIMATE) Trial
Primary Objective:	To determine the feasibility of recruiting 72 ARDS patients across sites given 1 year of active enrolment per site, as well as assess the rate of participant recruitment and understand the barriers to enrolment.
Secondary Objectives:	
 ➤ To assess adherence to our explicit mechanical ventilation protocols, with particular focus on delivered tidal volumes in both groups and measured ΔP and estimated ΔP_{L-dyn} in the ECMO group. ➤ To measure and understand the reasons for crossovers in each group.
Exploratory Objectives:	
 ➤ Monitor safety issues, recording Serious Adverse Events (SAEs) in both groups. ➤ Quantify cytokine levels to further understand the inflammatory processes involved.
Patient States:	
This domain will enrol patients in the following platform defined state;
 
 ➤ Intubated patients, not on extracorporeal life support, with high normalized respiratory system elastance (≥ 2.5 cm H₂O/(ml/kg predicted body weight)).
Study Design:	An interventional, open-label, randomized, multi-site feasibility study.
Duration:	The duration of this study will include an estimated 1 year of recruitment for each site to reach overall target sample size, and a 6 month post-randomization follow up for patients.
Planned Total Sample Size:	Approximately 72 evaluable patients will be randomized in this domain protocol.

Intervention:
	
Participants will be randomized to receive either the experimental group: ultra-protective ventilation facilitated by an ECMO device or the control group: conventional lung-protective ventilation (LPV).


Inclusion/Exclusion Criteria:
	
Patients will be eligible for randomization in this domain if they meet PRACTICAL platform eligibility criteria as well as ULTIMATE specific eligibility criteria.
 
PRACTICAL Inclusion Criteria:
 
 1. Acute hypoxemic respiratory failure meeting all of the following criteria; 
 ○ New or worsening respiratory symptoms developing within 2 weeks prior to the onset of need for oxygen or respiratory support, ○ Receiving any of the following types of oxygen or respiratory support for at least 4 hours prior to the time of randomization; supplemental oxygen at 10 L/min or higher, high flow nasal oxygen (at any flow rate), invasive ventilator support, extra-corporeal life support (ECLS), or non-invasive ventilator support, ○ Minimum FiO₂ ≥ 0.40 (for venturi mask, high flow nasal cannula, or invasive or non-invasive ventilation) or oxygen flow rate ≥10 L/min on face mask for at least 4 hours at the time of evaluation for eligibility unless already on extra-corporeal life support. 2. Age ≥ 18 years 
PRACTICAL Exclusion Criteria:
 
 1. Hypoxemia is primarily attributable to acute heart failure or fluid overload. 2. Hypoxemia is primarily attributable to pulmonary embolism. 3. Hypoxemia is primarily attributable to status asthmaticus.

	
4. Extubation is planned or anticipated on the day of screening.5. ICU discharge is planned or anticipated on the day of screening.6. The patient is moribund and deemed unlikely to survive past 24 hours (as determined by the clinical team).7. The patient is being transitioned to a fully palliative philosophy of care. 
ULTIMATE Inclusion Criteria:
 
1. Endotracheal mechanical ventilation for ≤ 5 days.2. Early moderate-severe hypoxemic respiratory failure with a $\text{PaO}_2/\text{FiO}_2 \leq 200$ mmHg for at least 6 hours. 
ULTIMATE Exclusion Criteria:
 
1. Patients over 65 years of age.2. Currently receiving any form of ECMO (ex. venovenous, venoarterial, or hybrid configuration).3. $\Delta P_{L-dyn} \leq 20$ or Static $\Delta P \leq 15$ cm H₂O while receiving V_T 6mL/kg (i.e. normalized elastance < 2.5 cmH₂O/mL/kg).4. Chronic hypercapnic respiratory failure defined as $\text{PaCO}_2 > 60$ mmHg in the outpatient setting.5. Home mechanical ventilation (non-invasive ventilation or via tracheotomy), not CPAP.6. Actual body weight exceeding 1kg per centimeter of height.7. More than 48 hours have passed since meeting inclusion criteria.8. Severe hypoxemia with $\text{PaO}_2/\text{FiO}_2 < 80$ mmHg for > 6 hours at time of screening.9. Severe hypercapnic respiratory failure with $\text{pH} < 7.15$ and $\text{PaCO}_2 > 60$ mmHg for > 6 hours at time of screening.
--	---

	
10. Expected mechanical ventilation duration <48 hours at time of screening.
 
11. Confirmed diffuse alveolar hemorrhage from vasculitis.
 
12. Contraindications to limited anticoagulation (ex. active GI bleeding, bleeding diathesis).
 
13. Pregnancy—due to unknown effects of PaCO₂ changes on placental blood flow.
 
14. Respiratory failure known or suspected to be caused by COVID-19.

Study Assessments:	Study assessments are depicted in the study schema (Section 5.2).
Safety Variables & Analysis:	The safety and tolerability of VV-ECMO will be evaluated by means of recording serious adverse events in both groups and monitoring the predicted physiological response (reduced driving pressure ΔP) to CO ₂ removal by VV-ECMO.
Efficacy Assessments & Analysis	The efficacy of VV-ECMO will be evaluated by means of assessing delivered tidal volumes in both groups and magnitude of physiological response (reduced driving pressure ΔP) to CO ₂ removal by VV-ECMO.
Statistical Analysis:	A target sample size of 72 ARDS patients will be randomized across sites given 1 year of active enrollment per site. This timeline will determine feasibility, as well as test the validity of our eligibility criteria, ventilation protocols, and study procedures. Descriptive statistical analyses and an intention-to-treat principle will be employed for the pilot phase of the trial.

TABLE OF CONTENTS

1	SYNOPSIS	4
2	List of Abbreviations	10
3	BACKGROUND	12
3.1	The problem to be addressed	12
3.2	Why is a trial needed now?.....	12
4	PRIMARY RESEARCH QUESTIONS AND STUDY OBJECTIVES	14
4.1	Definitive ULTIMATE Trial	14
4.2	The ULTIMATE Pilot Study	14
5	STUDY DESIGN	15
5.1	Patient population	15
5.2	PRACTICAL Platform Eligibility Criteria	15
5.2.1	PRACTICAL Inclusion Criteria.....	15
5.2.2	PRACTICAL Exclusion Criteria	15
5.3	ULTIMATE Domain Eligibility Criteria.....	16
5.3.1	Inclusion Criteria	16
5.3.2	Exclusion Criteria.....	16
5.4	Patient Consent.....	17
6	STUDY PLAN	18
6.1	Study Schedule.....	18
6.2	Study Schema.....	18
6.3	Optional Correlative Sample Collection	20
7	CONCOMITANT MEDICATION/ PROCEDURES	21
8	TRIAL INTERVENTIONS	22
8.1	Experimental Group: Ultra-protective Ventilation using ECMO devices.....	22
8.1.1	Stabilization and ECMO Initiation	22
8.1.2	Maintenance and Weaning of Ultra-Protective Ventilation	23
8.2	Control Group: Conventional Lung-Protective Ventilation (LPV)	24
8.3	Procedures Common to Both Groups – Experimental & Control	25
8.4	Crossovers.....	25

8.5	ECMO Study Device Supply	25
9	SAFETY AND REPORTING REQUIREMENTS	26
9.1	Serious Adverse Event	26
9.2	Reporting Serious Adverse Events	27
9.3	Procedures for Expedited Reporting	28
9.4	Reporting & Follow up of Serious Adverse Events	28
10	STATISTICAL ANALYSES	29
10.1	Study Population	29
10.2	Evaluation of Safety	29
10.3	Evaluation of Efficacy	30
10.4	Primary Objective	30
10.5	Primary Endpoint	30
10.6	Secondary Objectives	30
10.7	Secondary Endpoints	30
10.8	Exploratory Objectives	30
10.9	Exploratory Endpoints	31
10.10	Clinical Endpoints	31
10.11	Proposed Type of Analyses	31
10.12	Proposed Frequency of Analyses	31
10.13	Feasibility Outcomes	32
10.14	Sites	32
10.15	Randomization Scheme	32
11	PUBLICATION POLICIES AND DISCLOSURE OF DATA	33
11.1	Intellectual Property	33
11.2	Data Sharing	33
12	References	34

2 LIST OF ABBREVIATIONS

ABG	Arterial Blood Gases
AE	Adverse Event
ARDS	Acute Respiratory Distress Syndrome
aPTT	Activated Partial Thromboplastin
eCRF	Electronic Case Report Form
CPAP	Continuous Positive Airway Pressure
DSMB	Data Safety Monitoring Board
ΔP_{L-dyn}	Dynamic Trans-Pulmonary Driving Pressure
ECLS	Extra-corporeal Life Support
ECCO ₂ R	Extracorporeal CO ₂ Removal
FdO ₂	Fraction of Delivered Oxygen
FiO ₂	Fraction of Inspired Oxygen
ICU	Intensive Care Unit
MOP	Manual of Procedures
PaCO ₂	Partial pressure of carbon dioxide
PaO ₂	Partial pressure of Oxygen
PEEP	Positive End Expiratory Pressure
P _{PLAT}	Plateau Pressure
REB	Research Ethics Board
RCT	Randomized Controlled Trial
SAE	Serious Adverse Events
SDM	Substitute Decision Maker
SpO ₂	Percent Saturation of Oxygen
TEE	Trans-Esophageal Echocardiography

VILI	Ventilator Induced Lung Injury
V_T	Tidal Volume
VV-ECMO	Venovenous Extracorporeal Membrane Oxygenation

3 BACKGROUND

Complete background information of the **Platform of Randomized Adaptive Clinical Trials in Critical Illness (PRACTICAL) Randomized Control Trial** can be found in the Master Protocol.

3.1 The problem to be addressed

Acute Respiratory Distress Syndrome is an important public health problem.[1, 2] ARDS patients account for 10% of all ICU patients and 25% of all patients requiring invasive ventilation.[3] Mortality remains high, from 34 to 65%,[4] and up to 10,000 Canadians die with ARDS each year.[1, 5]

Ventilator-induced lung injury (VILI) contributes to ARDS mortality. While ventilators provide essential life support in ARDS, mechanical ventilation can also perpetuate lung injury.[6, 7] In a seminal RCT, a low tidal volume strategy reduced mortality from 40% to 31%, and this strategy is now considered to be the standard of care for ARDS.[8, 9] **However, usual care, standard ventilation is often still injurious.**[10] Driving pressure (ΔP) –a key marker for development of VILI– combines elements of tidal volume and lung compliance and is frequently elevated in clinical practice.[11] Attempts to lower driving pressure and lung stress further have been limited by hypoventilation and respiratory acidosis.[12]

Venovenous Extracorporeal Membrane Oxygenation (VV-ECMO) can facilitate ultra-low intensity mechanical ventilation through CO₂ removal. VV-ECMO is a technique that provides artificial respiratory support by adding O₂ and removing CO₂ from blood.[13]

3.2 Why is a trial needed now?

VV-ECMO reduces mortality in very severe ARDS patients and its use is rapidly expanding. In the largest and most recent RCT of VV-ECMO, mortality was reduced with VV-ECMO, and this was most pronounced in patients with higher baseline oxygen levels.[14] This suggests that the effect was mediated through VILI-reduction rather than avoiding death from hypoxemia per se. Driven by these positive results and a large increase in demand driven by the COVID-19 pandemic, many new centres are developing programs to deliver ECMO.

Ultra-low intensity ventilation facilitated by extracorporeal CO₂ removal (ECCO₂R) may indeed improve outcomes. There is good physiological rationale to believe that resting the lung further by reducing tidal volume, driving pressure, or respiratory rate– reducing mechanical power – could further lower the clinical impact of VILI.[15–17] Among 10,112 ventilated patients in the Toronto Intensive Care Registry, adjusted for baseline characteristics, higher mechanical power was associated with increased risk of death on any day of ventilation (HR 1.064; 95% CI 1.058 to

1.074 per J/min).[18] Reducing lung stress and strain is possible by transferring this work to the external artificial membrane lung on VV-ECMO.

At the current time the safest and most feasible manner to deliver CO₂ removal is through higher-flow VV-ECMO. We recently reported that a variety of modern ECCO₂R devices are capable of supporting ultra-low tidal volume ventilation.[19] However, secondary analysis of this study showed that when CO₂ removal was delivered through a VV-ECMO device with capability for higher flow and more CO₂ removal, patients were much more likely to reach V_T of 4 mL/kg (92 vs. 64%) and were less likely to experience complications of hemolysis or bleeding (6 vs 27%).[20] Although flow rates above 1.5L/min may not be required for ECCO₂R with these devices, standard VV-ECMO flows at 3-6L/min may be safer because they avoid the need for more aggressive anticoagulation, minimize pump recirculation and blood trauma,[21] and can support hypoxemia that may develop due to hypoventilation in the native lung.

To be effective ECCO₂R must use efficient devices *and* target patients who cannot be safely ventilated with usual standard-of-care ventilation. The recently published REST trial used a low-flow, low-efficiency ECCO₂R device in 412 unselected patients with moderate-severe hypoxemic respiratory failure.[22] There was no difference in mortality between groups, likely driven by fact that only modest reductions in intensity of ventilation were achieved. Tidal volume was only 2 mL/kg lower in the ECCO₂R, and moreover this reduced driving pressure by only 3 cm of H₂O. Recent work from our group shows reductions in driving pressure drive mortality benefit from tidal volume reduction,[23] and that driving pressure is reduced most by ECCO₂R in patients with low respiratory system compliance (high elastance)[24].

The uncritical adoption of ECCO₂R is premature and problematic. Wide dissemination of VV-ECMO outside the severe ARDS population tested in EOLIA at this time would represent premature adoption of a complex technology without rigorous evaluation of associated risks and benefits. A systematic review of ECCO₂R identified 14 studies (2 RCTs) including only 495 patients and concluded that there is a “paucity of high-quality data and significant variation in technology used among studies”.[25] Recent editorialists on the REST Trial also conclude that “Future studies that harness the potential benefits of ECCO₂R without increasing the risk of other complications are needed”.

In summary, ECCO₂R can facilitate ultra-low intensity ventilation while simultaneously avoiding harmful hypercapnia and acidosis. At the current time the safest and most feasible manner to deliver CO₂ removal is through higher-flow VV-ECMO. This approach, termed ‘ultra-protective’ ventilation, may indeed improve outcomes in patients with moderate-severe ARDS. We therefore propose the Ultra-Low Tidal Volume Mechanical Ventilation in ARDS Through ECMO (ULTIMATE) Trial.

4 PRIMARY RESEARCH QUESTIONS AND STUDY OBJECTIVES

4.1 Definitive ULTIMATE Trial

Primary Research Question:

What is the effect of ultra-protective ventilation facilitated by CO₂ removal through VV-ECMO versus best current standard ventilation on all-cause hospital mortality among patients with early moderate-severe hypoxemic respiratory failure receiving potentially injurious mechanical ventilation?

Secondary Research Questions:

Among these same patients, what is the effect of ultra-protective ventilation versus best current standard ventilation on: (1) duration of mechanical ventilation; (2) duration of ICU and hospital stay; (3) organ dysfunction; (4) barotrauma; and (5) mortality at other time-points (ICU discharge, 28-day, 60-day)?

4.2 The ULTIMATE Pilot Study

Before embarking on a definitive multinational trial to address the questions listed above, the ULTIMATE Pilot Study has these 3 specific feasibility objectives:

1. To assess the feasibility of recruiting 72 ARDS patients across sites over a period of 1-year of active enrollment per site, as well as estimate the rate of patient recruitment and understand barriers to recruitment;
2. To assess adherence to our explicit mechanical ventilation protocols, with particular focus on delivered tidal volumes in both groups and measured ΔP and estimated ΔP_{L-dyn} in the ECMO group; and lastly,
3. To measure and understand the reasons for crossovers in each group.

Our exploratory objectives include monitoring safety issues, by recording serious adverse events in both groups as well as quantifying cytokine levels to further understand the inflammatory processes involved.

If feasibility is demonstrated and major protocol changes are not required, patients randomized into the ULTIMATE Pilot Study will be rolled over and form the vanguard phase of the definitive ULTIMATE RCT.

5 STUDY DESIGN

The ULTIMATE Pilot Study is a multi-centre, randomized, open-label trial, embedded as a domain within the PRACTICAL platform trial. This domain will be conducted in compliance with the protocol and GCP guidelines.

5.1 Patient population

This domain will enrol patients in the following platform defined state;

- Intubated patients, not on extracorporeal life support (ECLS), with high normalized respiratory system elastance (≥ 2.5 cm H₂O/(ml/kg predicted body weight)).

Patients must meet both the PRACTICAL platform eligibility criteria (section 3.2) and the domain-specific ULTIMATE eligibility criteria (section 3.3) prior to randomization. Any questions about eligibility criteria must be addressed prior to patient randomization.

5.2 PRACTICAL Platform Eligibility Criteria

5.2.1 PRACTICAL Inclusion Criteria

1. Acute hypoxemic respiratory failure meeting all of the following criteria;
 - New or worsening respiratory symptoms developing within 2 weeks prior to the onset of need for oxygen or respiratory support,
 - Receiving any of the following types of oxygen or respiratory support for at least 4 hours prior to the time of randomization; supplemental oxygen at 10 L/min or higher, high flow nasal oxygen (at any flow rate), invasive ventilator support, extra-corporeal life support (ECLS), or non-invasive ventilator support,
 - Minimum FiO₂ ≥ 0.40 (for venturi mask, high flow nasal cannula, or invasive or non-invasive ventilation) or oxygen flow rate ≥ 10 L/min on face mask for at least 4 hours at the time of evaluation for eligibility unless already on extra-corporeal life support.
2. Age ≥ 18 years.

5.2.2 PRACTICAL Exclusion Criteria

1. Hypoxemia is **primarily** attributable to acute heart failure or fluid overload.
2. Hypoxemia is **primarily** attributable to pulmonary embolism.

3. Hypoxemia is **primarily** attributable to status asthmaticus.
4. Extubation is planned or anticipated on the day of screening.
5. ICU discharge is planned or anticipated on the day of screening.
6. The patient is moribund and deemed unlikely to survive past 24 hours (as determined by the clinical team).
7. The patient is being transitioned to a fully palliative philosophy of care.

5.3 ULTIMATE Domain Eligibility Criteria

5.3.1 Inclusion Criteria

1. Endotracheal mechanical ventilation for ≤ 5 days.
2. Early moderate-severe hypoxemic respiratory failure with a $\text{PaO}_2/\text{FiO}_2 \leq 200$ mmHg for at least 6 hours.

5.3.2 Exclusion Criteria

1. Patients over 65 years of age.
2. Currently receiving any form of ECMO (ex. venovenous, venoarterial, or hybrid configuration).
3. $\Delta P_{L-dyn} \leq 20$ or Static $\Delta P \leq 15$ cmH₂O while receiving V_T 6mL/kg (i.e. normalized elastance < 2.5 cmH₂O/mL/kg).
4. Chronic hypercapnic respiratory failure defined as $\text{PaCO}_2 > 60$ mmHg in the outpatient setting.
5. Home mechanical ventilation (non-invasive ventilation or via tracheotomy), not CPAP.
6. Actual body weight exceeding 1kg per centimeter of height.
7. More than 48 hours have passed since meeting inclusion criteria.
8. Severe hypoxemia with $\text{PaO}_2/\text{FiO}_2 < 80$ mmHg for > 6 hours at time of screening.
9. Severe hypercapnic respiratory failure with $\text{pH} < 7.15$ and $\text{PaCO}_2 > 60$ mmHg for > 6 hours at time of screening.
10. Expected mechanical ventilation duration < 48 hours at time of screening.
11. Confirmed diffuse alveolar hemorrhage from vasculitis.
12. Contraindications to limited anticoagulation (ex. active GI bleeding, bleeding diathesis).
13. Pregnancy—due to unknown effects of PaCO_2 changes on placental blood flow.
14. Respiratory failure known or suspected to be caused by COVID-19.

Eligible non-randomized patients will be identified and reasons for non-enrolment classified as:

1. Lack of consent from patient or substitute decision maker (specifying reason);
2. Refusal from attending physician (specifying reason);
3. Enrolment in a confounding RCT;
4. Research coordinator or device not available.

To better characterize the generalisability of our randomized population, baseline, demographic, and outcome data will be recorded on all eligible non-randomized patients.

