6.2 Study Schema

Required Procedures	Pre-Ventilation (Baseline)	Daily*	Day 1	Day 3	Day 7	ICU Discharge	At 6 months post-randomization (Phone Visit)
Window	N/A	N/A	N/A	N/A	N/A	N/A	±14 days
Consent & Randomization ¹	X						
Demographics ²	X						
Medical History ³	X						
Vitals ⁴	X	X					
Hemodynamics ⁵	X	X					
Respiratory Data ⁶	X	X					
Hematology ⁷	X	X					
Biochemistry ⁸	X	X					

Arterial Blood Gases (ABG) ⁹	X	X					
Pregnancy Test (urine/serum)	X						
Optional: Blood Sample Collection ¹⁰	X			X	X	X	
For the Control Arm: Conventional Lung Protective Ventilation ¹¹ per section 7.2		X					
For the Experimental Arm: ECMO Intervention ¹² per section 7.1		X					
MV Readiness to Wean	X	X					
Spontaneous Breathing Trial ¹³		X					
Sweep Gas Off Trials (SGOTs) ¹⁴		X					
HrQOL, Modified Rankin Scale and Vital Status							X ¹⁵
Glasgow Coma Scale and Sofa Score	X	X					
Serious Adverse Events ¹⁶			X				
Concomitant Medications ¹⁷	X						

¹ Consent should be obtained prior to any study-specific baseline assessments and according to site institutional timelines. Randomization in the ULTIMATE domain will occur for consenting eligible patients once elastance has been estimated as high (≥ 2.5 cmH₂O/ml/kg PBW) per indicated eligibility criteria.

² Demographics include age, gender, height, and weight. Race and ethnicity will be reported only for patients who have consented to the collection of this data.

³ Hospital admission (date/time), ICU admission (date/time), APACHE IV, Charlson Comorbidity Index, COVID-19 infection status

⁴ Vitals include temperature, heart rate, respiratory rate, and blood pressure.

⁵ Hemodynamics include BP, PAPm, PCWP, SvO₂ and will reported in the database if collected.

⁶ Respiratory data include mode of ventilation, FiO₂, PEEP, PIP, RR, ventilation rate, tidal volume, plateau and driving pressure, oxygen saturation, and expiratory occlusion pressure (P_{occ}).

⁷ Hematology reporting on Hg, WBCs, and platelets. If not done daily per clinical standard-of-care procedures, sites are not required to have these tests done exclusively for research purposes, and this will not be considered a protocol deviation.

⁸ Biochemistry will include reporting the following values: INR, PTT, activated clotting time, Fibrinogen, Antithrombin III, D-Dimers, plasma-free hemoglobin, sodium, glucose, creatinine, albumin, bilirubin, potassium, bicarbonate, creatinine kinase,

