8.1.1 Stabilization and ECMO Initiation

If not already done, patients will be deeply sedated to a Sedation Assessment Scale (SAS) = 1 and then be paralyzed with a neuromuscular blocking agent (NMBA). Baseline usual care standard ventilation will then be set as follows:

- Mode: Volume Assist-Control
- FiO₂ 1.0;
- PEEP 10-15 cm H₂O or higher as needed to maintain SpO₂>92%;
- V_T = 6 ml/kg PBW and adjusted to maintain P_{PLAT} ≤ 30 cm H₂O
- Inspiratory to expiratory (I:E) ratio 1:1 to 1:3, avoiding auto-PEEP
- Respiratory rate set to match previous minute ventilation to maximum of 35 bpm and targeting a pH above 7.15

These initial adjustments may occur over a period of a few minutes to a couple of hours, depending upon the baseline V_T and the ability of the patient to tolerate sudden changes. In keeping with routine clinical practices, an arterial blood gas should be drawn within 1 hour of transitioning onto the study protocol to assess both oxygenation and ventilation.

As soon as the patient is stable on these standard settings, the clinical team will measure the patient's respiratory elastance using the following equation:

$$Elastance = \frac{Driving\ Pressure}{\frac{Tidal\ Volume}{PBW}} = \frac{P_{plat} - PEEP\ total}{\frac{VT}{PBW}}$$

If the patient's static driving pressure is 15 cmH₂O or lower, then re-assess patient within a 12-hour timeline for ECMO initiation whilst keeping the patient deeply sedated and paralyzed. If patient's static ΔP is 16 cmH₂O or higher, then proceed with cannulation and connection to the VV-ECMO circuit using sterile technique and monitoring according to usual practice (e.g. ultrasound-guided puncture, radiography, trans-esophageal echocardiography (TEE), or

fluoroscopic cannula positioning). We recommend use of the study-supplied dual-lumen bicaval Crescent cannula connected to the Nautilus oxygenator, but the clinical team may choose any VV-ECMO configuration that facilitates 3-5 L/min blood flow.

VV-ECMO will then be initiated with pump speed set to deliver blood flow of 3-5 L/min and sweep gas flow of 1 L/min of 100% oxygen.

The mechanical ventilator will then be adjusted as follows:

- Mode: Pressure Control
- FiO₂ 0.5
- Set Driving Pressure to 10
- PEEP 10-15 cm H₂O
- Inspiratory time 0.7-1 second
- Respiratory rate 10

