8.1.2 Maintenance and Weaning of Ultra-Protective Ventilation

Deep sedation, paralysis, and these low-intensity mechanical ventilation settings will be maintained for at least 48 hours after ECMO initiation. The clinical team will make adjustments to the VV-ECMO settings to maintain the same PaCO₂, pH and PaO₂ and SpO₂ targets as above. These adjustments to VV-ECMO sweep gas or blood flow will be dictated by ABG results drawn as clinically indicated.

On study day 3, patients will then enter the maintenance and weaning phase – neuromuscular blockade will be discontinued, and lighter sedation levels (SAS 2-3) will be targeted unless otherwise decided by the attending physician.

During the first 7 days after randomization and once neuromuscular blockade is stopped and patients are making spontaneous breathing efforts, we will use sweep gas flow (primary) and sedation (secondary) to modulate spontaneous efforts to maintain low intensity ventilation, targeting the estimated dynamic trans-pulmonary driving pressure (ΔP_{L-dyn}) and tidal volume.

Clinicians will measure patient respiratory effort by calculating ΔP_{occ} (which is always zero or negative):[26]

- Perform expiratory hold and record trough pressure with next effort (record as = PEEP if no efforts made)
- Calculate $\Delta P_{occ} = \text{trough pressure} - \text{PEEP}$
- Calculate $\Delta P_{L-dyn} = (\text{Peak airway pressure} - \text{PEEP}) - 0.67 \times \Delta P_{occ}$

To maintain $\Delta P_{L-dyn} \leq 23$ cm H₂O while maintaining a V_T of 8 ml/kg PBW or lower, the treating team will adjust in the following order: a) the mechanical ventilator, b) the sweep gas flow, and c) sedation levels. After day 7 driving pressure and V_T targets, as well as sweep gas settings will be determined by the attending physician.

We will wean ECMO prior to liberating from mechanical ventilation and provide explicit protocols for weaning ECMO (See Manual of Procedures). Briefly, patients will be assessed daily for ability to discontinue ECMO – all patients who are not paralyzed and are breathing spontaneously on sweep gas flow of 4 L/min or less, and who are receiving an FiO₂ of ≤ 0.6 on the mechanical ventilator with a PaO₂/FiO₂ > 150 will undergo a trial of sweep gas off on ECMO. ECMO will be discontinued if patients tolerate sweep gas off for at least 12 hours (i.e., no significant hypoxemia, respiratory acidosis, or work of breathing).

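### Exclusion 3 is not the elastance cut-off it claims to restate: it conflicts with it at a static driving pressure of 15, its dynamic limit has no fixed elastance equivalent, and its *or* is undefined

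*Protocol*

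**What the plan says.** Four places in the protocol set or use the threshold.

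- **Entry state.** Section 5.1 enrols intubated patients "with high normalized respiratory system elastance (≥ 2.5 cm H₂O/(ml/kg predicted body weight"), and the synopsis gives the same state. Section 6.2, footnote 1, allows randomisation "once elastance has been estimated as high (≥ 2.5 cmH₂O/ml/kg PBW) per indicated eligibility criteria".
- **Exclusion 3.** Section 5.3.2, repeated in the synopsis, excludes ΔP_L-dyn of 20 or less or static ΔP of 15 cmH₂O or less, measured "while receiving V_T 6mL/kg (i.e. normalized elastance < 2.5 cmH₂O/mL/kg").
- **Definitions.** Section 8.1.1 defines elastance as plateau pressure minus total PEEP, divided by tidal volume per kg predicted body weight. Section 8.1.2 defines ΔP_L-dyn as peak airway pressure minus PEEP, minus 0.67 times the occlusion pressure ΔP_occ, which is zero or negative.
- **Start of the intervention.** Section 8.1.1 uses the static measure only. If the "static driving pressure is 15 cmH₂O or lower, then re-assess patient within a 12-hour timeline for ECMO initiation"; at 16 or higher the team proceeds.

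Two uses of eligibility matter here. The primary endpoint (section 10.5) records patients randomised and patients eligible but not randomised, and evaluates the validity and impact of the criteria. Section 10.11 says that, if accrual is marginal, the number excluded under each criterion will be examined and criteria that remove many patients reconsidered.

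**The concern.** The abbreviation i.e. in exclusion 3 presents the pressure limits and the elastance limit as one rule. If they differ, a screener who applies the pressures and a screener who applies the elastance figure can reach opposite decisions on the same patient, each following the text. Those decisions feed the eligible-but-not-randomised count in the primary endpoint and the count for exclusion 3 that section 10.11 would use to revise eligibility. In a pilot meant to test its own eligibility criteria, differences in how sites read one criterion would be mixed with real differences in case mix and consent.

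**Working it through.** **Inputs.** V_T 6 mL/kg, static limit 15 and dynamic limit 20 (section 5.3.2); elastance cut-off 2.5 (sections 1, 5.1, 5.3.2, 6.2); formulas for elastance (8.1.1) and ΔP_L-dyn (8.1.2). The peak-to-plateau gap, R, is not in the protocol and is varied as an assumption.

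**Step 1: static limit.** Elastance E = static ΔP / (V_T/PBW).

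- ΔP 15: 15/6 = 2.50. This reproduces the protocol's figure, but only as a value; the inequality signs do not match.
- ΔP 16: 16/6 = 2.67.

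A patient at exactly 15 is classified as follows:

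| Rule | Decision at ΔP 15, E 2.50 |
|---|---|
| Entry state, E ≥ 2.5 (1, 5.1, 6.2 footnote 1) | In |
| Exclusion 3, static ΔP ≤ 15 | Excluded |
| Gloss inside exclusion 3, E < 2.5 | Not excluded |
| Section 8.1.1, ≤ 15 versus ≥ 16 | Re-assess; do not proceed directly |

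So a patient randomised at 2.50 to the experimental group would not go directly to the intervention if V_T and ΔP stayed the same.

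**Step 2: dynamic limit.** Take a passive patient (ΔP_occ = 0) with set PEEP equal to total PEEP. Then ΔP_L-dyn = peak − PEEP = (plateau − PEEP) + R = 6E + R. The limit ΔP_L-dyn ≤ 20 becomes E ≤ (20 − R)/6.

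| R (cmH₂O, assumed) | Elastance equivalent of ΔP_L-dyn ≤ 20 |
|---|---|
| 0 | 20/6 = 3.33 |
| 1 | 19/6 = 3.17 |
| 2 | 18/6 = 3.00 |
| 3 | 17/6 = 2.83 |
| 4 | 16/6 = 2.67 |
| 5 | 15/6 = 2.50 |
| 6 | 14/6 = 2.33 |

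The dynamic limit matches the stated 2.5 only at R = 5. Effort moves it again: with peak − PEEP held at 16, ΔP_occ of −6 gives 16 + 0.67 × 6 = 20.02, just above the limit, whereas no effort gives 16, below it.

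**Step 3: meaning of *or*.**

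- *Either limit excludes.* A passive patient with static ΔP 16 (E 2.67) and R = 3 has ΔP_L-dyn 19. The patient is in the entry state, yet excluded. The same patient with R = 5 has ΔP_L-dyn 21 and is not excluded. The overlap runs from 2.50 to (20 − R)/6. It is at most 3.33, and at R = 5 or more only the static conflict at 2.50 is left.
- *Each limit applies in one breathing state.* If the static limit governs passive patients, their conflict is the single point 2.50. For patients making breathing efforts, the dynamic limit still has no fixed relation to elastance 2.5.

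The protocol does not say which reading applies.

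**The case against.** The strongest defence has four parts.

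1. **Exclusions narrow an entry state by design.** Section 5.1 requires platform and domain criteria together, and footnote 1 points to the eligibility criteria, so being in the state and also excluded is not in itself a contradiction. That is right in general. It does not rescue exclusion 3, because the conflict at 15 lies between that criterion's own limit and its own gloss.
2. **The protocol's usage suggests a reading by breathing state.** Section 8.1.1 uses static ΔP alone for paralysed patients, and section 8.1.2 brings in ΔP_L-dyn once patients breathe spontaneously. This is plausible and would confine the passive-patient conflict to one value. But section 8.1.2 also covers patients making no effort, and no eligibility passage states the split.
3. **The static rule is clear in practice.** The division in section 8.1.1 at 15 versus 16 agrees with the 15-or-less limit, so on whole-number readings only one value is ambiguous. That stands as a limit on size. Section 5.1 also requires eligibility questions to be addressed before randomisation, which helps only if the site sees a question.
4. **Consequences are bounded.** The number randomised, and the criterion of at least 60 recruited (section 10.13), are plain counts and remain interpretable. No formal inference is planned. This stands.

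A reader might infer that everyone with elastance from 2.5 to 3.3 is both eligible and excluded. The protocol does not support that: 3.33 needs no peak-to-plateau gap, no effort and the either-limit reading of *or*. A reader might also put a percentage on those affected, but the protocol gives no distribution of ΔP and no value for R, so any such figure would come from the assumptions.

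**Conclusion.** The point holds. Exclusion 3 is wrong as written in three respects:

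- **Boundary.** Static ΔP 15 (elastance 2.50) gets contradictory answers on any reading for a passive patient. This follows from the protocol's own formula and needs no assumption.
- **Equivalence.** The elastance gloss does not hold for ΔP_L-dyn. In a passive patient the corresponding elastance depends on R: 3.33 at R = 0, 3.00 at R = 2, 2.50 at R = 5. This assumes no effort and set PEEP equal to total PEEP.
- **Connective.** *Or* has two tenable meanings. One adds an overlap above 2.5 of unknown width, at most up to 3.33; the other leaves passive patients with the single point 2.50.

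The number of patients affected cannot be computed from the protocol. The effect falls on the eligible-but-not-randomised count and on the per-criterion exclusion counts. It does not make the primary endpoint as a whole uninterpretable, and a shift in population between the pilot and the definitive trial would be speculation: section 4.2 carries pilot patients forward only if no major protocol change is needed.

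**What to change.** Reconcile the synopsis (patient state and exclusion 3) with sections 5.1, 5.3.2, 6.2 footnote 1 and 8.1.1:

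1. Use one boundary sign, so that a static ΔP of 15 at 6 mL/kg and an elastance of 2.50 receive the same decision everywhere.
2. State whether *or* means that either limit excludes, or that each limit applies in a different breathing state; in the second case, say which applies when.
3. Remove the elastance equivalence for ΔP_L-dyn. If it is kept for the static limit, make its sign agree.

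The sponsor's clinical leads choose the measure and the cut-off; the statistical requirement is only that every place gives the same answer for the same patient.

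The cost is a short eligibility amendment and a screening-log update, with no new measurements. It is best done before the screening counts accumulate.
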